12.6.1.1 Analysis of Unsolicited AEs

The following summaries of unsolicited AEs by SOC and PT are further provided, separately for AEs occurring within the first 28 days after each vaccination, within 28 days after any vaccination, and all reported AEs (including those reported later than 28 days after any vaccination):

- Occurrence of unsolicited AEs
- Occurrence of related unsolicited AEs
- Occurrence of unsolicited AEs by maximum severity (mild / moderate / severe)
- Occurrence of related unsolicited AEs by maximum severity (mild / moderate / severe)

Additionally, a summary of unsolicited AEs (excluding solicited AEs) occurring within the first 28 days after each vaccination and within 28 days after any dose that have a frequency of > 5% in at least one treatment arm (on PT level) by SOC and PT is provided. The summary is repeated for all reported AEs (including those reported later than 28 days after any vaccination).

Summaries of unsolicited AEs occurring within 28 days after each vaccination and within 28 days after any vaccination are provided based on the SAS 2. Summaries of all reported unsolicited AEs (including those reported later than 28 days after any vaccination) are provided based on the SAS.

Listings of unsolicited AEs and related unsolicited AEs are produced. These listings exclude solicited AEs and flag treatment emergent event.

12.6.1.2 Analysis of Solicited AEs

The following summaries of solicited AEs within 7 days after each trial vaccination and within 7 days after any trial vaccination are planned:

- Summary of local and systemic AEs, overall and by maximum grade (mild / moderate / severe)
 - Are also provided by gender (female/male) for any vaccination, vaccination 1, and vaccination 2.

-
- Occurrence of local AEs, overall and by maximum grade (mild / moderate / severe)
 - Occurrence of systemic AEs, overall and by maximum grade (mild / moderate / severe)
 - Occurrence of related systemic AEs, overall and by maximum grade (mild / moderate / severe)
 - Duration (days) of local AEs, overall and for grade 3 events
 - Duration (days) of systemic AEs, overall and for grade 3 events
 - Duration (days) of related systemic AEs, overall and for grade 3 events
 - Daily summary of local AEs overall and by maximum grade (mild/moderate/severe) (only for each dose)
 - Daily summary of systemic AEs overall and by maximum grade (mild/moderate/severe) (only for each dose)
 - Daily summary of related systemic AEs overall and by maximum grade (mild/moderate/severe) (only for each dose)
 - Summary of time of onset (Day) overall and for grade 3 solicited AEs, any solicited AEs, local, systemic AEs, and related systemic AEs
 - Time of onset (Day) of local AEs, overall and for grade 3 events
 - Time of onset (Day) of systemic AEs, overall and for grade 3 events.
 - Time of onset (Day) of related systemic AEs, overall and for grade 3 events

All analyses of solicited AEs are provided based on the SASsol.

In agreement with the sponsor was decided to not provide any analyses on solicited AEs in the EOT analysis. Therefore some of the above analyses are never performed. For details, please refer to Appendix 4.

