### 4.2 Endpoints

#### 4.2.1 Primary Endpoints

##### Primary Safety Endpoints

- Occurrence, intensity and relationship of medically-attended AEs collected through 6 months after the second trial vaccination in all subjects.
- Occurrence, intensity and relationship of SAEs and AESIs collected through 1 year after the second trial vaccination in all subjects.
- Occurrence of fatal SAEs through 1 year after the second trial vaccination in all subjects.
- Occurrence of AEs leading to vaccine withdrawal or trial discontinuation through 1 year after the second trial vaccination in all subjects.
- Occurrence, intensity and duration of each solicited local AE within 7 days after each trial vaccination in a subset of subjects.
- Occurrence, intensity, duration of each solicited systemic AE within 7 days after each trial vaccination in a subset of subjects.
- Occurrence, intensity and relationship of unsolicited AEs occurring within 28 days after each trial vaccination in a subset of subjects.

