## 10.3 Statistical Analyses

### 10.3.1 General Considerations

Two analyses are planned: the interim (triggered by regulatory requirements to obtain early conditional approval in Europe, and the advancement of the accrual of a pre-defined number of COVID-19 cases in Trial CV-NCOV-004) and the final (on all data up to Day 393 visit). A SAP for both analyses will be prepared and finalized at the latest prior to database locks. This document will provide further details regarding the definition of analysis variables and analysis methodology to address all trial objectives and the handling of missing data.

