- Section 7.2.2: Secondary immunogenicity objective on lot-to-lot consistency was deleted.
- Section 7.3: All exploratory objectives were deleted.
- Section 8.2: Added EOT wording for placebo subjects after study unblinding.
- Section 8.5.2: Adapted Sample information on primary immunogenicity objective to new analysis scope.
- Section 8.6: Updated unblinding information according to protocol 3.0 and study development.
- Section 9.1.2: Reduced timepoints for immunogenicity analyses to Days 1, 29 and 43.
- Section 9.2.1: Reduced secondary efficacy endpoints according to scope reduction in EOT delivery.
- Section 9.2.2: Reduced timepoints for immunogenicity analyses to Days 1, 29 and 43. Reduced secondary immunogenicity endpoints according to scope reduction in EOT delivery.
- Section 9.3: Deleted all exploratory endpoints.
- Section 9.4: Updated "Estimands" table to match study.
- Section 9.5.2: Updated IS definition to not exclude subjects who had received an AV prior to 15 days after 2nd vaccination.
- Section 9.5.4: Reduced PPI Set to 250 subjects.
- Section 9.5.6: Mentioned that EASS is not further applicable.
- Section 9.5.7: Updated and corrected Summary of Analysis Sets
- Section 10.5.5: Corrected AESI definition
- Section 10.5.8: Added Section defining overreported AEs.
- Section 10.6, and 10.6.1: Updated wording according to protocol v 3.0 and for clarity reasons
- Section 10.6.2.3 and 10.6.3: Deleted Sections on seroconversion to N protein antibodies and CMI.
- Section 10.7.1.1 and 10.7.2 and 10.7.5: Provided for a local instead of a central laboratory being used
- Section 10.10: Added unblinding column to censoring table.
- Section 10.11: Updated overview table to match analysis updates.
- Section 11.0: Updated IA info to match study development.
- Section 12.0 and 12.2 and 12.4.2 and 12.6.1.2: Updated to match study development and reduced EOT analysis.
- Section 12.6.1.4: Added section on repeats of AE analyses without censoring
- Section 12.6.7: Added section on adapting the safety analyses to the requirements of extensive unblinding
- Section 12.7 and 12.7.1: Reduced timepoints for immunogenicity analyses to Days 1, 29 and 43.
- Section 12.7.2 and 12.8.1.1 – 12.8.1.4: Adapted to account for reduced EOT analyses.
- Section 12.7.3 and 12.8.2: Deleted to account for endpoint deletion.

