6.0 Introduction

The SAP describes the statistical methods to be used during the reporting and analyses of data collected under CureVac AG Protocol CV-NCOV-005.

The SAP should be read in conjunction with the trial protocol version 5.0 dated 22-Dec-2021 and Case Report Form (CRF) v4.0 dated 10-Jun-2021.

This SAP describes the statistical methods used for the final analysis. The SAP v1.0 is approved prior to the first relevant delivery¹. Changes following approval of the first version of the SAP are tracked in the SAP Change Log and the last final SAP version is approved prior to final database lock.

Each version of the SAP requires approval by the Sponsor.

It must be noted that all main stakeholders from the combined Sponsor and designated Contract Research Organization (CRO) (PRA/ICON) study team have been unblinded between approval of SAP versions 3.0 and 4.0. As a consequence, the SAP version 4.0 is created and approved by an unblinded authorship/approval team.

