9.0 Trial Endpoints

9.1 Primary Endpoints

9.1.1 Primary Safety Endpoints

- Occurrence, intensity and relationship of medically-attended AEs collected through 6 months after the second trial vaccination in all subjects.

-
- Occurrence, intensity and relationship of SAEs and AESIs collected through EOT Visit in all subjects.
 - Occurrence of fatal SAEs through EOT Visit in all subjects.
 - Occurrence of AEs leading to vaccine withdrawal or trial discontinuation through EOT Visit in all subjects.
 - Occurrence, intensity and duration of each solicited local AE within 7 days after each trial vaccination in a subset of subjects.
 - Occurrence, intensity, duration of each solicited systemic AE within 7 days after each trial vaccination in a subset of subjects.
 - Occurrence, intensity and relationship of unsolicited AEs occurring within 28 days after each trial vaccination in a subset of subjects.

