
 Occurrence, intensity and relationship of unsolicited AEs occurring within 28 days after each trial vaccination in a subset of subjects. 	
 Each solicited systemic AE within 7 days after each trial vaccination by intensity, by relationship to trial vaccine and overall. At least 1 unsolicited AE, at least 1 grade 3 unsolicited AE and each unsolicited AE by SOC/PT occurring within 28 days after each trial vaccination and overall by causal relationship to trial vaccine and overall. 
The mean duration in days by group with standard deviation (SD) of solicited AEs is described.

Primary Immunogenicity	

SARS-CoV-2 RBD of S protein antibody responses
 
On Days 1, 29 and 43:
 
 Serum antibodies to SARS-CoV-2 RBD of S protein. Occurrence of seroconversion to SARS-CoV-2 RBD of S protein 
 Seroconversion is defined as detectable SARS-CoV-2 RBD of S protein antibodies in the serum of subjects who tested seronegative at baseline. 	
In subjects belonging to the Immunogenicity/Reactogenicity subset and evaluable {complying with the definition of PPI Subset}:
 
On Days 1, 29 and 43:
 
 Geometric Mean of Titers (GMTs) with 95% Confidence Interval (CI) of SARS-CoV-2 RBD of S protein antibody responses by group and by baseline serostatus. 
On Days 29 and 43 for subjects seronegative at baseline:
 
 Number and percentage with exact 95%CI of subjects by group for whom a seroconversion is observed (detectable SARS-CoV-2 RBD of S protein antibodies in the serum).
Secondary Efficacy	

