12.0 Statistical Methods

Unless otherwise noted, categorical variables are summarized using counts and percentages. Percentages are presented with one decimal place, except 100% is displayed without any decimal places and percentages are not displayed for zero counts. Continuous variables are summarized using the number of observations (n), mean, median, SD, 1st Quartile (Q1), and 3rd Quartile (Q3), minimum and maximum values. Mean, median, Q1 and Q3 are presented to 1 decimal more than original data. SD is presented with 2 decimals more than original data. Minimum and maximum match the decimal points in the original data. The maximum number of decimals is 4, unless otherwise stated.

In general, all data summaries are presented overall and by vaccine group. Thereby, the CVnCoV data is presented for pooled CVnCoV lots and split by lot. Efficacy outputs are not split by lot and do not have an overall column presented. Selected outputs are **additionally** presented using further subsetting of the data. This is specified explicitly in the respective sections.

If not stated otherwise, p-values from statistical tests are two-sided and CIs are calculated using a 95% confidence level.

Age group is used as a factor for stratification of randomization. The efficacy analyses are in general **not** adjusted for this factor.

No imputation of missing data other than that described in Section 10.3 is performed.

All data collected during this trial is displayed in data listings, unless otherwise specified. Screening failures are excluded from all listings and tables if not otherwise stated. Listings include all relevant assigned/derived variables. If not explicitly stated, listings do not show imputed data, but present data as reported.

All data summaries and tabulations are prepared using SAS® Version 9.4 or higher.

In agreement with the sponsor it was decided to not perform some of the analyses in the EOT analysis. Therefore some of the below analyses were never performed. For details, please refer to Appendix 4

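### SAP v4.0 keeps solicited AEs as primary safety endpoints but plans no solicited-AE analysis at end of trial, and section 6.1 neither lists nor explains this departure from protocol v5.0

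*SAP*

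**What the plan says.** Protocol v5.0, section 4.2.1, lists seven primary safety endpoints. Two concern solicited events; the local one reads "Occurrence, intensity and duration of each solicited local AE within 7 days after each trial vaccination in a subset of subjects". Section 10.3.5 sets out the tabulations: frequency by maximum intensity, relationship to vaccine for systemic events, time to onset, duration, and subjects with at least one local or systemic event after each vaccination. Section 10.3.1 names two analyses, the interim "and the final (on all data up to Day 393 visit").

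SAP v4.0 keeps the endpoints. Section 9.1.1 repeats the systemic one as "Occurrence, intensity, duration of each solicited systemic AE within 7 days after each trial vaccination in a subset of subjects", the estimand table in 9.4 adds "The mean duration in days by group with standard deviation (SD) of solicited AEs is described", and Table 3 in 9.5.7 assigns both endpoints to SASsol. Section 12.6.1.2 lists 14 types of solicited-AE summary. It then states that, with the sponsor's agreement, it "was decided to not provide any analyses on solicited AEs in the EOT analysis. Therefore some of the above analyses are never performed", and refers to Appendix 4, which is held outside the SAP.

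There are two other traces. Section 12.0 says in general terms: "In agreement with the sponsor it was decided to not perform some of the analyses in the EOT analysis". The v4.0 change-history entry covering 12.6.1.2 says "Updated to match study development and reduced EOT analysis". Section 6.1, which lists changes from protocol, has 17 items, and none concerns solicited AEs. Section 6.0 records that "the SAP version 4.0 is created and approved by an unblinded authorship/approval team".

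**The concern.** A primary endpoint that stays in the endpoint list, the estimand table and the analysis-set table should have a result in the final analysis, or a recorded reason why not. SAP 6.0 says the plan describes the final analysis, and sections 8.2 and 11.0 say there is no formal interim. The one formal analysis left therefore has no table of ordinary reactogenicity by grade and duration.

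Section 6.1 is where a reader would look for such a change. Items 12 to 17 disclose individual dropped or reduced analyses: the lot comparison, severity classes, SAS repeats, N seroconversion, vaccine efficacy on burden of disease, and Kaplan-Meier curves. All are secondary or sensitivity analyses. The one cut that affects primary endpoints is absent.

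Reasons are given elsewhere: protocol 9.4.2 and 9.4.3 explain why the N-protein efficacy analysis and the CMI analysis lost their value. Because an unblinded team wrote and approved this SAP version, a recorded reason matters more than usual.

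**Working it through.** **1. Does another end-of-trial output fill the gap?**

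| Section | What it covers | Solicited AEs |
|---|---|---|
| SAP 12.6.1.1 | Unsolicited AEs | Not covered |
| SAP 12.6.1.3 | SAEs, AESIs, medically attended AEs, intercurrent conditions, withdrawals, fatal AEs, SMQ/CMQ terms | Only if they also fall in one of these categories |
| SAP 12.6.1.4 and 12.6.7 | Repeats without censoring: unsolicited AEs, SAEs, unsolicited AESIs, fatal AEs | Only if serious or fatal |

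Ordinary injection-site pain, fever or fatigue, by grade and duration, has no end-of-trial table and would appear only in listings.

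**2. How many subjects could be affected?** The planned subset is the first 1,260 enrolled (840 CVnCoV, 420 per lot). SAP 12.6.6 describes a safety delivery when the first 1,037 subjects are six weeks past dose 2. The footnote in SAP 6.0 describes a rolling-submission delivery with a matching six-week trigger; that the two are the same is an inference. If the tables were limited to those 1,037 and no other delivery covered the rest, 1,260 − 1,037 = 223 subjects are missing, and 223/1,260 = 17.7%. If the rest were covered, the number is 0.

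**3. What would the 223 case cost?** The plan's own figure first. Protocol Table 5 gives a 98.5% chance of seeing at least one AE of true incidence 5:1000 with N = 840:

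- 1 − (1 − 0.005)^840 = 98.5%, reproduced.
- Zero-event 95% bound: 1 − 0.05^(1/840) = 3.56:1000, stated as 3.6:1000.

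Assuming a 2:1 split among the 1,037, CVnCoV N = 1,037 × 2/3 = 691 pooled and 1,037/3 = 346 per lot:

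- Detection at 5:1000: 1 − 0.995^691 = 96.9%.
- Zero-event bound: 1 − 0.05^(1/691) = 4.3:1000.
- Relative interval width: √(840/691) = 1.10.

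Reaction rates are not in the documents, so a range is assumed. Half-widths are 1.96 × √(p(1 − p)/N), in percentage points:

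| Rate | Pooled, N = 840 | Pooled, N = 691 | Per lot, N = 420 | Per lot, N = 346 |
|---|---|---|---|---|
| 1% | 0.67 | 0.74 | 0.95 | 1.05 |
| 10% | 2.03 | 2.24 | 2.87 | 3.16 |
| 50% | 3.38 | 3.73 | 4.78 | 5.27 |

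**4. Which tables does the protocol need?** Protocol 10.3.5 maps onto occurrence by maximum grade, duration and time to onset, each for local, systemic and related systemic AEs (3 × 3 = 9), plus the summary of any local or systemic AE. That is 10 of the 14 listed types. The daily summaries and the overall onset summary go beyond it.

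**5. The lot ratio (separate and minor).** With 100 subjects per lot and an assumed log10 SD of 0.4 to 0.6, the 95% CI of the Day 43 GMC ratio is the ratio times or divided by 10^(t(198) × SD × √(2/100)) = 1.29 to 1.47. Rebuilding it from the two by-lot intervals that SAP 12.7 retains gives 10^(√2 × t(99) × SD/10), which is also 1.29 to 1.47 and at most 0.3% wider. What is lost is the protocol's restriction to RBD-negative subjects, because SAP 12.7 splits by N serostatus.

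**The case against.** Solicited AEs are collected for seven days after each dose, so follow-up to Day 393 adds no new onsets, and a data scope of everything to Day 393 need not mean re-tabulating every endpoint. Earlier tabulation is likely. Section 12.6.1.2 says only that some analyses are never performed, section 12.6.6 has all safety outputs repeated without censoring at the earlier delivery, and the April 2021 change history added solicited AEs by gender. Appendix 4 would settle the matter and is not available here. The omission is also stated in the governing section itself.

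Most of this stands, and it rules out several stronger readings:

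- **That solicited AEs were never analysed.** The wording implies that some were.
- **That 223 subjects are missing.** The 1,037 is worded as a timing trigger, not as the set analysed. By the schedule, 11 February 2021 plus 28 plus 42 days is 22 April; anyone first dosed by about 18 March would by then be seven days past dose 2. Recruitment dates and the data cut are not given.
- **That unblinded results drove the choice.** Nothing in the documents shows this, and safety is descriptive without testing.
- **That SAP 12.6.7 item 1 contradicts 12.6.1.2 by calling the analyses unchanged.** That item refers to the analyses as described above it, which can include the exemption.

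What the objection does not remove is the explicit end-of-trial rule for two retained primary endpoints, its absence from 6.1, and the missing reason. A reader of the protocol and SAP cannot tell where, or on whom, these endpoints are reported.

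**Conclusion.** The point holds as a departure that is unlisted in 6.1 and unexplained, leaving two primary safety endpoints without a planned table in the final analysis. The number of subset subjects in no solicited-AE table is unknown, between 0 and 223 of 1,260. The upper end rests on the earlier delivery being limited to 1,037 subjects and on no other delivery covering the rest; the figures for that case also assume a 2:1 split. Even then the loss of precision is modest, with intervals about 10% wider. The weight lies in the missing full-subset result and the missing record. It is worth correcting because the tables are already specified and the data already collected.

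The lot ratio is minor. Its removal is disclosed as item 12 of 6.1, but protocol v5.0 keeps it as objective, endpoint, estimand and analysis (4.1.2, 4.2.2, 4.3, 10.2.3, 10.3.6), no reason is given, and SAP Table 3 still lists it.

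**What to change.** In the final analysis, run the 10 tables identified above once on the full final SASsol, for each dose and for any dose. Add the end-of-trial decision to 6.1 for whatever remains dropped. If an earlier delivery already covered the full subset with these tables, no re-run is needed: cite that delivery and the reason in 6.1 instead.

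For the lots, either compute the Day 43 RBD GMC ratio with its two-sided 95% CI in PPI subjects who received both doses from the same lot and were RBD-negative at baseline, descriptively and without a margin, or give the reason in item 12 and remove the leftover row from Table 3.

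The cost is one added item in 6.1, one run of tables already specified, and at most one ratio on the immunogenicity data already planned for analysis. The downside is a longer report and possibly a second set of solicited-AE percentages that must be explained beside those of the earlier delivery.

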12.6.1.3 Analysis of AEs (Combined Unsolicited and Solicited)

An overall summary of unsolicited AEs, SAEs, intercurrent medical conditions affecting immune response, AESIs, medically attended AEs, AEs leading to vaccine withdrawal, AEs leading to withdrawal from trial and AEs with fatal outcome is prepared for AEs occurring within 28 days after each vaccination, within 28 days after any vaccination, and all reported AEs (including those reported at more than 28 days after any vaccination), presenting the number and percentage of subjects with

- any unsolicited AEs ,
- related unsolicited AEs,
- grade 3 (severe) unsolicited AEs
- grade 3 (severe) related unsolicited AEs
- SAEs (includes solicited AEs),
- related SAEs (includes solicited AEs),
- intercurrent medical conditions affecting immune response (includes solicited AEs),
- AESIs (includes solicited AEs),
- related AESIs (includes solicited AEs),
- medically attended AEs (includes solicited AEs),
- related medically attended AEs (includes solicited AEs),

-
- AEs leading to vaccine withdrawal (includes solicited AEs),
 - AEs leading to withdrawal from trial (includes solicited AEs),
 - AEs with fatal outcome (includes solicited AEs),
 - related AEs with fatal outcome (includes solicited AEs).

The overall summary is also provided by gender (male/female) for any vaccination, vaccination 1 and vaccination 2.

The following summaries of AEs by SOC and PT are further provided, separately for AEs occurring within the first 28 days after each vaccination, within the 28 days after any vaccination, and all reported AEs (including those reported at more than 28 days after any vaccination):

- Occurrence of SAEs,
- Occurrence of related SAEs,
- Occurrence of SAEs by maximum severity (mild / moderate / severe),
- Occurrence of related SAEs by maximum severity (mild / moderate / severe),
- Occurrence of intercurrent medical conditions affecting immune response,
- Occurrence of AESIs,
- Occurrence of related AESIs,
- Occurrence of medically attended AEs,
- Occurrence of related medically attended AEs,
- Occurrence of AEs leading to vaccine withdrawal,
- Occurrence of AEs leading to withdrawal from trial,
- Occurrence of AEs with fatal outcome,
- Occurrence of related AEs with fatal outcome,
- Occurrence of SMQs and CMQs (as specified in Section 10.5.7). (The SMQ/CMQ tables are only provided for all reported AEs, not by vaccination 1 and vaccination 2 separately and only by PT, not by SOC.)

All summaries and listings above are provided based on the SAS.

A listing of all SAEs and all SAEs with fatal outcome is further provided by subject, including both unsolicited and solicited AEs.

Further AE listings supporting the AE tables described above include both relevant solicited and unsolicited AEs.

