9.4 Estimands

Table 2 **Error! Reference source not found.** presents the study endpoints and corresponding Estimands based on the study protocol, Section 4.3.

Table 2: Study Endpoints and Estimands

ENDPOINTS (subject level)	ESTIMANDS (population level)
Primary Safety	

 • Occurrence, intensity and relationship of medically-attended AEs collected through 6 months after the second trial vaccination in all subjects. • Occurrence, intensity and relationship of SAEs and AESIs collected through EOT Visit in all subjects. • Occurrence of fatal SAEs through EOT Visit in all subjects. • Occurrence of AEs leading to vaccine withdrawal or trial discontinuation through EOT Visit in all subjects. • Occurrence, intensity and duration of each solicited local AE within 7 days after each trial vaccination in a subset of subjects. • Occurrence, intensity, duration and relationship of each solicited systemic AE within 7 days after each trial vaccination in a subset of subjects. 	
In subjects who received at least 1 dose of CVnCoV or placebo vaccine, the number and percentage of subjects by group reporting at least 1 and of each type {by System Organ Class (SOC)/ Preferred Term (PT)} of:
 
 • Medically-attended AE collected through 6 months after the second trial vaccination overall, by intensity and by causal relationship to trial vaccine. • SAE collected through EOT Visit overall and by causal relationship to trial vaccine. • AESI collected through EOT Visit overall, by intensity and by causal relationship to trial vaccine. • Fatal SAE collected through EOT Visit. • At least 1 AE leading to vaccine withdrawal or trial discontinuation through EOT Visit. 
In subjects who received at least 1 dose of CVnCoV or placebo vaccine, and belong to the Immunogenicity/Reactogenicity subset, the number and percentage of subjects by group reporting:
 
 • Each solicited local AE within 7 days after each trial vaccination by intensity and overall.

ENDPOINTS (subject level)	ESTIMANDS (population level)

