9.5.7 Summary of Analysis Sets to be Used per Analysis

Table 3 and

Table 4 provide an overview on the Analysis Sets used for the analyses of each endpoint.

Table 3: Summary of Analysis Sets to be Used per Analysis - Safety and Immunogenicity Endpoints

Endpoint Type	Endpoint Short Description	Analysis Set
Primary safety endpoint	Occurrence, intensity and relationship of medically-attended AEs	SAS
	Occurrence, intensity and relationship of SAEs and AESIs	SAS
	Occurrence of fatal SAEs	SAS
	Occurrence of AEs leading to vaccine withdrawal or trial discontinuation	SAS
	Occurrence, intensity and duration of solicited local AEs	SASsol
	Occurrence, intensity and duration of solicited systemic AEs	SASsol
	Occurrence, intensity and relationship of unsolicited AEs	SAS 2
Primary Immunogenicity Endpoint	Serum antibodies to SARS-CoV-2 RBD of S protein	PPI
	Seroconversion to SARS-CoV-2 S RBD protein	PPI#
Secondary Immunogenicity Endpoint	Serum neutralizing antibodies to SARS-CoV-2 virus	PPI
	Seroconversion to SARS-CoV-2 virus	PPI#
	Lot-to-Lot consistency of 2 CVnCoV lots, based on antibodies to the SARS-CoV-2 RBD of S protein	PPI#

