10.5 AEs

An AE is any untoward medical occurrence in a subject which does not necessarily have to have a causal relationship with the investigational product. In this trial, confirmed cases of COVID-19 and complications/sequelae are not considered as AEs as they are captured on the CRF pages for COVID-19 illness which are expected outcomes of the trial and are analyzed as efficacy endpoints.

In this trial, for subjects in the Immunogenicity/Reactogenicity Subset, information on solicited local and systemic AEs occurring within 7 days after each vaccination and on unsolicited AEs occurring within 28 days after each vaccination are collected.

For all trial subjects, information on medically attended AEs through 6 months after second vaccination and SAEs, AESIs and AEs leading to vaccine withdrawal or trial discontinuation through EOT are recorded.

Non-serious intercurrent medical conditions that may affect the immune response to vaccination are also collected as AEs throughout the trial.

No other AEs require recording in the CRF.

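### The 28-day overall AE summary in SAP 12.6.1.3 counts unsolicited AEs on the full SAS, although they are collected completely only in the 1,260-subject subset

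*SAP*

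**What the plan says.** SAP 12.6.1.3 describes an overall table that "is prepared for AEs occurring within 28 days after each vaccination, within 28 days after any vaccination, and all reported AEs". It has 15 rows. The first four are any, related, grade 3 and grade 3 related unsolicited AEs. The other 11 cover SAEs, AESIs, medically attended AEs, intercurrent conditions, AEs leading to withdrawal and fatal AEs. A second version is planned: "The overall summary is also provided by gender (male/female) for any vaccination, vaccination 1 and vaccination 2". The section closes its table list with "All summaries and listings above are provided based on the SAS". SAP 12.6.1 takes the number of subjects in the analysis set as the usual percentage base; for tables after dose 2 it is those in the set who received dose 2.

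Elsewhere the same 28-day endpoint is given to the subset:

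- SAP 12.6.1.1: unsolicited-AE summaries for 28 days after each dose and "within 28 days after any vaccination are provided based on the SAS 2". Only the all-reported version goes on the SAS.
- SAP 9.5.7, Table 3: the row "Occurrence, intensity and relationship of unsolicited AEs" is assigned to SAS 2.
- SAP 9.4: the estimand is for subjects who were dosed "and belong to the Immunogenicity/Reactogenicity subset, the number and percentage of subjects by group reporting", among other items, "At least 1 unsolicited AE, at least 1 grade 3 unsolicited AE and each unsolicited AE by SOC/PT occurring within 28 days".
- Protocol 10.2.2 and protocol Table 6: unsolicited AEs on SAS 2.

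On collection, SAP 10.5 and 10.5.4 gather 28-day unsolicited AEs from the Immunogenicity/Reactogenicity Subset. For all subjects SAP 10.5 lists medically attended AEs, SAEs, AESIs, AEs leading to withdrawal or discontinuation, and intercurrent conditions, and ends: "No other AEs require recording in the CRF".

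**The concern.** The four unsolicited rows combine a numerator that is complete in only about half the subjects with a denominator that counts all of them. The percentages will be too low in every group. Under 1:1:1 randomization the shortfall should be similar across groups, so a vaccine-placebo ratio may be roughly kept, but absolute rates and absolute differences shrink. Reactogenicity and tolerability are usually read from absolute rates, and readers often go first to the overall summary.

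The report would also give two values for the same primary safety quantity: the share of subjects with an unsolicited AE within 28 days in the 12.6.1.1 tables on SAS 2, and a lower figure for that quantity in the 12.6.1.3 table on the SAS. None of the changes from protocol listed in SAP 6.1 moves these rows to the SAS, so this reads as a catch-all sentence that was not checked against its first four rows.

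**Working it through.** **1. The plan's own denominators for unsolicited AEs.** SAP 8.5.1, Table 1 uses the subset sizes, 840 CVnCoV subjects and 420 per lot. With 1-(1-p)^N:

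- N = 840, p = 5:1000: 98.5% (stated 98.5%).
- N = 420, p = 5:1000: 87.8% (stated 87.8%).
- N = 1,680, p = 1:1000: 81.4% (stated 81.4%; this is the all-subjects column).

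The sample-size section therefore already treats the subset as the population for these AEs.

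**2. Planned sizes.** SAP 8.1 gives about 2,520 subjects, 840 per group, so the SAS holds 1,680 CVnCoV and 840 placebo. The subset is the first 1,260 enrolled (SAP 9.5.2). One third per group is 420, so SAS 2 holds 840 CVnCoV and 420 placebo.

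**3. Dilution.** Let P be the subset percentage and q the recorded rate outside the subset divided by P. Then

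SAS % = (1,260·P + 1,260·q·P) / 2,520 = P·(1+q)/2.

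The documents do not give q. It should exceed zero, because SAEs, AESIs and medically attended AEs are recorded in everyone, and because the post-vaccination steps for the other subjects (protocol 9.1.2.1 and 9.1.2.2) ask for new AEs to be noted. It should be below 1, because those subjects have no 28-day unsolicited diary (protocol Table 2 against Table 1).

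**4. Illustration.** Assumed subset rates: 40% CVnCoV (336/840) and 25% placebo (105/420), same q in both groups.

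| q | Factor | CVnCoV on SAS | Placebo on SAS | Difference (points) | Ratio |
|---|---|---|---|---|---|
| SAS 2 (correct) | 1 | 40.0% | 25.0% | 15.0 | 1.60 |
| 0 | 0.500 | 336/1,680 = 20.0% | 105/840 = 12.5% | 7.5 | 1.60 |
| 0.25 | 0.625 | (336+84)/1,680 = 25.0% | 131.25/840 = 15.6% | 9.4 | 1.60 |
| 0.50 | 0.750 | (336+168)/1,680 = 30.0% | 157.5/840 = 18.75% | 11.25 | 1.60 |

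**5. Unequal capture.** The ratio is kept only if q is the same in both groups. With an assumed q of 0.1 on CVnCoV and 0.3 on placebo, the SAS shows 40 × 0.55 = 22.0% and 25 × 0.65 = 16.25%, a ratio of 1.35 instead of 1.60.

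**6. Does another rule repair this?** The overreporting rule in SAP 10.5.8 removes late events from tables. It leaves 28-day events in non-subset subjects in place and does not change the denominator.

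**The case against.** The strongest reply is that the endpoint itself is handled correctly. Table 3, the estimand and 12.6.1.1 all use the subset, and 12.6.1.1 gives occurrence, relationship and maximum severity, which is the content of the four rows. Eleven of the 15 rows are collected in all subjects and belong on the SAS. Safety is descriptive, and the plan does not call for risk differences. This stands, and it limits the harm to a misleading table rather than a lost result. It does not make the four percentages right.

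The size is also uncertain. Actual enrolment is not given. Because the subset is the first 1,260 enrolled, any shortfall falls outside it: the general factor is (1,260 + q(N-1,260))/N, and with an assumed N of 2,000 it would be 0.63 at q = 0. In the earlier delivery on the first 1,037 subjects (SAP 12.6.6), everyone should lie inside the subset, so there is no dilution there. q may differ by row; grade 3 events, for example, may be medically attended more often. Protocol 9.3.3.2 limits recording of volunteered AEs to the all-subject categories, so it adds nothing to the evidence for partial capture.

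Finally, Appendix 4, the list of outputs, is held outside the SAP. It may name another set or show that some versions are not produced. SAP 12.6.1.4 does schedule an uncensored 28-day overall summary at end of trial, but names no set for it. If Appendix 4 says SAS 2, it contradicts 12.6.1.3, and the SAP wording still needs correcting.

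**Conclusion.** The concern holds. As written, SAP 12.6.1.3 puts the four unsolicited-AE rows of the 28-day overall summary on a population in which those AEs are not completely collected, against the estimand, Table 3, 12.6.1.1 and the protocol. At planned sizes the percentages are 0.50 to 0.75 of the subset values for q between 0 and 0.50, and absolute differences shrink by the same factor when q is equal across groups. The result rests on planned sizes and on an assumed q; the 40% and 25% rates only illustrate it. The matter should be fixed before the final tables are produced, but it does not threaten the primary safety result.

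**What to change.** - In SAP 12.6.1.3, base the any, related, grade 3 and grade 3 related unsolicited rows of both 28-day versions of the overall summary on SAS 2, and print that N beside the rows. Do the same in the by-gender version.
- In SAP 12.6.1.4, name SAS 2 for the unsolicited rows of the uncensored 28-day overall summary.
- Keep the SAS for SAEs, AESIs, medically attended AEs, intercurrent conditions, fatal AEs and AEs leading to withdrawal.
- Leave the all-reported unsolicited tables and the 12.6.7 repeats on the SAS, since they carry valid all-subject data. Add a footnote that AEs starting within 28 days of a dose were fully collected only in the subset, or split those AEs by subset membership. The all-reported version of the overall summary can be treated the same way.
- Check Appendix 4 against the revised text.

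The cost is SAP wording, a population flag for four rows in existing programs, and two denominators in one table. The reported percentages will be higher, and so less favourable, than under the current wording.
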